Note: Can be performed up to 7 days post Baseline/Day 1. Liver biopsy obtained during the current hospitalization (including transfers between hospitals) prior to Screening is acceptable. However, if biopsy results are not consistent with AH, the subject will stop study drug within 3 days of receipt of the liver biopsy result, attend an EoT visit as soon as possible, and have a follow-up visit 30 days after their last dose of study drug, prior to being withdrawn from the study. If the liver biopsy sample is inadequate to confirm a pathologic diagnosis of AH and no alternative diagnosis is suggested on biopsy, then the subject may remain in the study.

• Record any serious adverse events (SAEs) and all adverse events related to protocol-mandated procedures occurring after signing of the consent form

From the time of obtaining informed consent through the first administration of investigational medicinal product, record all SAEs, as well as any adverse events related to protocol-mandated procedures on the adverse events case report form (eCRF). All other untoward medical occurrences observed during the Screening period, including exacerbation or changes in medical history are to be captured on the medical history eCRF. See Section 7 Adverse Events and Toxicity Management for additional details.

Subjects must meet all of the inclusion criteria and none of the exclusion criteria prior to randomization into the study.

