6.2.2. Baseline / Day 1 Assessments and Randomization

After review of inclusion and exclusion criteria to confirm eligibility, subjects will be randomized to study drug assignment and receive their Subject Identification Number via the IWRS prior to their first dose of study drug.

Randomization will be stratified by MELD < or ≥ 25 at Screening as calculated using local laboratory tests and an online MELD calculator (see Section 6.9.7).

During the entire hospitalization period, subjects will be evaluated daily with assessments to include a review of adverse events, concomitant medications, study drug adherence, and a symptom-directed PE including assessments for ascites and HE. Findings based on these assessments and laboratory investigations obtained by treating physicians as part of routine care will be assessed by the investigator for triggers that may necessitate further evaluation and/or treatment discontinuation and managed accordingly per Section 7.5 of the protocol.

The following will be performed and documented at the randomization visit prior to dosing:

- Review inclusion/exclusion criteria and confirm eligibility
- QoL Questionnaire (CLDQ)

- Assess alcohol consumption
- Complete PE including vital signs and body weight
- Perform standard 12-lead ECG
- Assessments for HE, ascites, HRS, and infection
- Obtain blood samples for:
 - Hematology
 - Chemistry: ALT, AST, albumin, alkaline phosphatase, bicarbonate, BUN, calcium, chloride, creatinine, glucose, LDH, magnesium, phosphorus, potassium, sodium, total and direct bilirubin, total protein, uric acid, GGT. Samples should be drawn for central and local laboratory testing for the calculation of the Lille Score (Section 6.9.12)
 - Coagulation Tests: PT, PTT, and INR. Samples should be drawn for central and local laboratory testing for calculation of the Lille Score (Section 6.9.12)
 - Blood and Urine for Biomarkers
 - ELF^{TM} Test and LOXL2
 - Insulin
 - Hemoglobin A1c
 - Lipid Profile
 - Sparse PK Sample (collected after dosing)
 - ___ PPD
- Urine pregnancy test (for females of childbearing potential)
- Collect stool for microbiome testing
- Record all concomitant medications that the subject has taken since the previous visit
- Record any SAEs and all adverse events occurring after signing of the consent form
- Randomization via IWRS (Note: stratification assignment is based on MELD score as calculated using local laboratory results and an online MELD calculator (see Section 6.9.7).

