6.9.9. Infection

The occurrence of bacterial, fungal, or viral infections should be recorded as adverse events. Relevant data to be recorded include the source of infection, date of onset/resolution, presence of fever (temperature $\geq 38^{\circ}$ C/100.4°F), laboratory investigations (e.g. white blood cell count, cultures, chest x-ray), and anti-microbial therapy. An infection will be considered definite in subjects with clinical evidence of infection and a positive culture from a normally sterile source (with the exception of spontaneous bacterial peritonitis [SBP] as below). All other infections will be considered probable. In subjects with ascitic fluid neutrophils ≥ 250 cells/mm³, definite SBP will be recorded irrespective of culture positivity.

If pneumonia develops during the study, treatment according to the following guidelines is recommended:

- Community-Acquired Pneumonia: Infectious Diseases Society of America/American Thoracic Society Consensus Guidelines (2007) (http://cid.oxfordjournals.org/content/44/Supplement 2/S27.full)
 - The minimum recommended duration of antibiotic treatment is 5 days.
- Hospital-Acquired Pneumonia (HAP): Infectious Diseases Society of America/American Thoracic Society Consensus Guidelines (2016) (http://www.idsociety.org/Guidelines/Patient_Care/IDSA_Practice_Guidelines/Infections_by Organ System/Lower/Upper Respiratory/Hospital-Acquired Pneumonia (HAP)/)
 - HAP is defined as a pneumonia not incubating at the time of hospital admission and occurring \geq 48 hours after admission.
 - The minimum recommended duration of antibiotic treatment is 7 days.

SBP, UTI, and other infections that develop during the study should be treated according to the following guidelines:

- SBP: AASLD Practice Guidelines: Management of Adult Patients with Ascites Due to Cirrhosis: Update 2012. (http://www.aasld.org/publications/practice-guidelines-0#practice_guidelines_accordion-block-2). The minimum recommended duration of antibiotic treatment is 5 days. Patients with SBP who also have a serum creatinine
 1 mg/dL, blood urea nitrogen > 30 mg/dL, or total bilirubin > 4 mg/dL should also receive 1.5 g albumin per kg body weight within 6 hours of detection and 1.0 g/kg 2 days later.

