7.2.2. Assessment of Severity

The severity grading of AEs will be assessed as Grade 1, 2, 3, or 4 according to the Common Terminology Criteria for Adverse Events (CTCAE) Version 4.03, which can be found at http://evs.nci.nih.gov/ftp1/CTCAE/CTCAE_4.03_2010-06-14_QuickReference_5x7.pdf.

For AEs associated with laboratory abnormalities, the event should be graded on the basis of the clinical severity in the context of the underlying conditions; this may or may not be in agreement with the grading of the laboratory abnormality.

The distinction between the seriousness and the severity of an adverse event should be noted. Severe is a measure of intensity; thus, a severe reaction is not necessarily a serious reaction. For example, a headache may be severe in intensity, but would not be classified as serious unless it met one of the criteria for serious events listed above.

7.3. Investigator Requirements and Instructions for Reporting Adverse Events and Serious Adverse Events to Gilead

Requirements for collection prior to study drug initiation:

After informed consent, but prior to initiation of study medication, the following types of events should be reported on the case report form (eCRF): all SAEs and adverse events related to protocol-mandated procedures.

Adverse Events

Following initiation of study medication, collect all AEs, regardless of cause or relationship, until 30 days after last administration of study IMP must be reported to the eCRF database as instructed. During the post-treatment follow-up period (through Week 24), AEs including SAEs related to protocol mandated procedures must be collected and reported to the eCRF database.

All AEs should be followed up until resolution or until the adverse event is stable, if possible. Gilead Sciences may request that certain AEs be followed beyond the protocol defined follow up period.

Serious Adverse Events

All SAEs including deaths, regardless of cause or relationship, that occurs after the subject first consents to participate in the study (ie, signing the informed consent) until 30days after the last dose of study IMP must be reported to the eCRF database and Gilead Drug Safety and Public Health (DSPH) as instructed. This also includes any SAEs resulting from protocol-associated procedures performed after informed consent is signed. During the post-treatment follow-up period (through Week 24) any SAEs deemed related to the use of study IMP should also be reported.

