## 5.2. Other Baseline Characteristics

Prior alcohol consumption (g/day) before acute AH event, weight (kg), height (cm), and BMI (kg/m^2) as a continuous and categorical (< 25, 25 to < 30 and  $\ge 30$  kg/m^2) variable will be summarized separately by treatment group and sex and sex overall.

**Baseline characteristics** for the study will include the following:

- Baseline height (cm)
- Baseline weight (kg)
- Baseline BMI  $(kg/m^2)$
- Baseline BMI (< 25, 25 to < 30 and  $\geq$  30 kg/m^2)
- Prior alcohol consumption (g/day) before the acute AH event
- Alcohol Use Disorders Identification Test (AUDIT) as a continuous variable
- AUDIT as a categorical variable (< 8 [does not meet criteria]; ≥ 8 and <13 for women or

   <15 for men [harmful or hazardous drinking]; ≥ 13 for women, ≥ 15 for men [alcohol dependence])

- Severity of Alcohol Dependence Questionnaire (SADQ) as a continuous variable
- SADQ as a categorical variable (<16 [mild physical dependency]; 16-30 [moderate dependence];  $\geq$  31 [severe alcohol dependence])
- Method of liver biopsy (percutaneous, transjugular, missing)

- Biopsy consistent with AH diagnosis (yes, no)
- Fibrosis assessment method (Metavir-equivalent, Ishak, Not Available)
- Fibrosis score as a subcategory to the fibrosis method (ie, Metavir-equivalent [F0, F1-F2, F3, F4] or Ishak [F0, F1-F2, F3-F4, and F5-F6])
- Baseline ascites (none, mild/moderate [or diuretic responsive], severe [or diuretic refractory])
- Baseline hepatic encephalopathy (none, grade 1-2 [medication controlled], grade 3-4 [medication refractory])
- Hospitalized at screening (yes, no)
- Days hospitalized prior to first dose date. Calculated as: (minimum of [date of first dose of study drug, date of release] hospital admission date) +1 for subjects hospitalized at screening
- Baseline pyrexia (baseline temperature ≥ 38° C, ≥ 100.4° F [yes] or < 38° C, < 100.4 ° F [no])

- Baseline infection (yes, no) as recorded on the medical history eCRF.
- Treatment for baseline infection (yes, no) as recorded on the medical history eCRF
- Evidence of baseline infection on chest X-ray (yes, no)
- Baseline MELD score (as a continuous variable)
- Baseline CPT score (as a continuous variable)
- Baseline CPT class (A [scores of 5-6], B [scores of 7-9], C [scores of 10-15])
- Baseline Maddrey DF score (as a continuous variable)
- Baseline AST (U/L)
- Baseline ALT (U/L)
- Baseline AST/ALT Ratio
- Baseline total bilirubin (mg/dL)

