## 5.4. Medical History and Baseline Infections

General medical history data will be collected at screening and listed only. General medical history data will not be coded. Subjects with baseline infections will have a checkbox marked on the MH eCRF to denote baseline infection events, and baseline infections will be listed separately. Results from cultures, x-rays, and ascitic fluid neutrophil cell counts (ie, > 250 cells/mm^3) for spontaneous bacterial peritonitis (SBP) confirming reported infections during the screening period will be included on this listing.

Prior medications that were used to treat baseline infections will be identified as drugs with a pull down indication of "infection" on the CM eCRF. Medications with an end date prior to screening date or a start date that is after the first dosing date of SEL/PLA will be excluded.

Listings will be provided for chest X-rays, and liver imaging performed at the screening visit.

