#### 6.2.7. Events of Interest

The number and percentage of subjects with the following 2 types of events will be summarized:

- Infections of Interest (as described in Section 6.9.9 of the study protocol)
- Hepatorenal Syndrome events (meeting International Ascites Club criteria as described in Section 6.9.8 of the study protocol)

A postbaseline infection of interest will be considered to be "definite" in subjects with clinical evidence of infection (ie, AE with the infection field marked 'yes' on the AE eCRF) and a positive culture from a normally sterile source; infiltrate on chest x-ray and treatment with antibiotics; or ascitic fluid neutrophils  $\geq 250$  cells/mm^3, regardless of culture positivity for SBP. All other infections will be considered to be "probable". Results from laboratory investigations

will be used to enter the most specific AE verbatim term possible for coding purposes (ie, "*E. Coli* urinary tract infection" for a urinary tract infection where the pathogen "*E. Coli*" was present in a urine culture); and to serve as source documentation of the methods used to determine that the infection was "definite".

A summary of postbaseline "infections" (ie, adverse events that have 'yes' marked for infection on the AE eCRF) will be presented by treatment group, high level group term (HLGT) and lower lever term (LLT) from the MedDRA dictionary separately for infections that are "definite" infections and for those that are "definite/probable" infections. Multiple events reported within a HLGT, and LLT will be counted once only per subject in each summary. Infections will be summarized in alphabetic order of HLGT and then by LLT in descending total frequency within each HLGT. Infections with postbaseline onset dates or worsening on or after the first dose date of study drug through end of study will be summarized.

Culture and x-ray results collected for documenting definite infections will be presented alongside the reported infection in a listing sorted by start date for the infection and procedure date for the culture/x-ray. Cultures collected on/after Study Day 1 will be listed.

Postbaseline medications used to treat infections (identified from an indication of "Infection" on the CM eCRF) will be summarized by treatment group and preferred name. Medications with stop dates prior to first dose date of SEL/PLA will be excluded.

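### Baseline infection is taken from the medical history eCRF alone, so a serious or procedure-related infection starting between consent and first dose is coded as no baseline infection

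*SAP*

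**What the plan says.** SAP 5.2 defines the baseline item as "Baseline infection (yes, no) as recorded on the medical history eCRF". SAP 5.4 gives the mechanism: "Subjects with baseline infections will have a checkbox marked on the MH eCRF to denote baseline infection events". SAP 3.4 then uses the flag as a subgroup factor for death by Day 28 and Week 8 and for Lille category.

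The protocol decides which form an infection is written on. For the interval from consent to first dose, Protocol 6.2.1 tells sites to "record all SAEs, as well as any adverse events related to protocol-mandated procedures on the adverse events case report form (eCRF". The rest goes elsewhere: "All other untoward medical occurrences observed during the Screening period, including exacerbation or changes in medical history are to be captured on the medical history". Protocol 7.3 gives the same pre-dose reporting scope: "all SAEs and adverse events related to protocol-mandated procedures".

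For the infection endpoint, SAP 6.2.7 uses adverse event records whose infection field is marked yes, limited in time: "Infections with postbaseline onset dates or worsening on or after the first dose date of study drug through end of study will be summarized".

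**The concern.** The two documents split screening infections differently. The protocol splits them by seriousness and by relation to study procedures. The SAP assumes that every baseline infection is on the medical history form. An infection that the protocol places on the adverse event form before dosing has no route into the SAP's baseline flag.

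The accuracy of a descriptive baseline variable and of one exploratory subgroup split is at stake. The error would run in one direction: subjects with a serious or procedure-related infection in screening would move from the infected to the uninfected category. SAP 5.4 identifies prior drugs for baseline infection separately, from the indication on the concomitant medication form. Table 15.8.3.2.5 could therefore show anti-infective treatment in a subject whom the baseline table calls uninfected.

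**Working it through.** No figure in the plan depends on this point, so there is nothing to recompute. The check follows an infection through the written rules according to when it began and what kind it is.

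| Onset and type | Form (protocol) | Baseline infection (SAP 5.2, 5.4) | Postbaseline infection (SAP 6.2.7) |
|---|---|---|---|
| a. Before consent | Medical history (7.1.1) | Yes | Only if it worsens after dosing starts |
| b. Consent to first dose, neither serious nor procedure-related | Medical history (6.2.1) | Yes | Only if it worsens |
| c. Consent to first dose, serious | Adverse event (6.2.1, 7.3) | **No** | Only if it worsens |
| d. Consent to first dose, procedure-related | Adverse event (6.2.1, 7.3) | **No** | Only if it worsens |
| e. On or after first dose | Adverse event (7.3) | Not applicable | Yes |

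Rows c and d are the gap. The last column is right for both, because an infection that began before treatment should not count as postbaseline unless it worsens. The error is confined to the baseline column.

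**Can row c occur?** Yes. The synopsis (Study Procedures, Sepsis) screens every subject for infection and lets a subject be randomized within the screening period once the infection has been treated and judged controlled. Screening can last up to 14 days. Protocol 7.1.2 makes an event serious if, among other criteria, it lengthens an inpatient stay. A new infection during an inpatient screening period can meet that criterion in a subject who is later dosed.

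**Is the boundary of the gap clear?** Not fully. Protocol 6.2.2, at the randomization visit, says "Record any SAEs and all adverse events occurring after signing of the consent form". Protocol 6.9.9 says "The occurrence of bacterial, fungal, or viral infections should be recorded as adverse events". Footnote e of Appendix 2, attached to an infection row that includes Screening, also asks for findings to be recorded as adverse events. None of these has a seriousness limit, and they are hard to square with 6.2.1. A site that followed them could put row b infections on the adverse event form too, which would widen the gap.

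**Does another rule close it?** No. Chest X-ray evidence of infection is a separate baseline item in SAP 5.2 and does not feed the flag. Treatment for baseline infection has the same medical-history-only source.

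**Where do rows c and d still appear?** In the summary by treatment group of adverse events before first dose (SAP 7.1.6, Table 15.11.2.4.1), in Listing 16.2.7.1 and, for row c, in the serious adverse event Listing 16.2.7.3.1.

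**How many subjects?** Neither document gives a count or rate for rows c or d, so the extent of misclassification cannot be computed.

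**The case against.** The best defence is that SAP 5.4 means the checkbox to cover all screening infections. It has no exclusion for serious events, and its listing includes cultures, X-rays and ascitic fluid counts from the screening period. Protocol 6.2.1 says where a serious event is reported and does not forbid ticking the checkbox as well. The eCRF and its completion guidelines are not in the documents, so sites may have done both. That is possible, but no text requires double entry, and Protocol 6.2.1 reserves medical history for what is left after serious and procedure-related events are removed. A derivation should not depend on an unstated habit.

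The second defence is low impact, and it stands. Baseline infection is one of 16 baseline factors explored descriptively in SAP 3.4. It is not a stratification factor, and SAP 5.2 plans no formal testing of baseline characteristics.

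A reader might infer that an infection imbalance between the arms could be hidden. The documents do not support that. Rows c and d are tabulated by arm in Table 15.11.2.4.1, and the drugs recorded as treatment for baseline infection appear in Table 15.8.3.2.5. A discrepancy would be visible to anyone who compared the tables.

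**Conclusion.** The gap is real as the documents are written, and it is narrow. A subject is miscoded only if the infection began after consent, began before first dose, and was serious or procedure-related. This assumes that sites followed Protocol 6.2.1 and did not also tick the medical history checkbox. The number may be small or zero. The outputs affected are the baseline infection item in the baseline tables and the infection split in Tables 15.9.4.1 to 15.9.4.5. The primary safety analysis and the postbaseline infection endpoint do not change.

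Two stronger conclusions should not be drawn. A reader might infer that these infections drop out of the report altogether. They do not: they remain in the pre-dose adverse event table and the listings, and worsening after dosing is counted.

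A reader might also try to size the effect from Protocol 1.1, which cites 20% infected at admission and 90-day mortality of about 45% in infected against about 5% in uninfected patients. Those figures do not fit. Infection present at admission, where admission precedes consent, goes correctly to medical history. The mortality contrast is not specific to infections treated and controlled before randomization. The planned subgroup tables report death by Day 28 and Week 8 and Lille category, not 90-day death. No share of serious screening infections is given either.

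**What to change.** In SAP 3.4, 5.2 and 5.4, define baseline infection as the medical history infection checkbox OR an adverse event eCRF record with the infection field marked yes and onset before the first selonsertib/placebo dose. This cut-off meets the one in SAP 6.2.7, so every dated infection on the adverse event form has a place. Add the new records to Listing 16.2.4.3.4, report by arm how many subjects change category, and state how the companion item on treatment for baseline infection will be filled for them.

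SAP 2.3 says that treatment assignments were unblinded for the primary analysis. The rule should therefore be documented as a post-unblinding change. It is treatment-neutral, since it uses only the form, the infection field and the onset date.

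The cost is one derivation line and a rerun of the affected tables and listing. Both source fields are already described in SAP 5.4 and 6.2.7, so no new data collection is needed, provided the infection field was completed for pre-dose adverse event records. The recording instructions in Protocol 6.2.1, 6.2.2, 6.9.9 and Appendix 2 footnote e should also be reconciled, at least in a note in the study report.

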## Alcohol Consumption Level and Alcohol Dependence

The *Alcohol Use Disorders Identification Test (AUDIT)* is a screening tool developed by the World Health Organization (WHO) to assess alcohol consumption, drinking behaviors, and alcohol-related problems. AUDIT is comprised of 10 questions, with scores for each question ranging from 0 to 4. The total score (sum of a subject's scores across each of the 10 individual questions) for AUDIT will be summarized as a continuous variable and for the categories: < 8 (does not meet criteria);  $\ge 8$  and <13 for women or <15 for men (harmful or hazardous drinking) or  $\ge 13$  for women,  $\ge 15$  for men (alcohol dependence).

The *Severity of Alcohol Dependence Questionnaire (SADQ)* is a short, self-administered, 20-item questionnaire developed by the Addiction Research Unit at the Maudsley Hospital to measure severity of dependence on alcohol. Each question is assigned a score based on the subjects response (0 [almost never/not at all], 1 [sometimes/slightly], 2 [often/moderately], or 3 [nearly always/quite a lot]). Total score (sum of scores for the subject across the 20 questions) for SADQ will be summarized as a continuous variable and for the categories: <16 (mild physical dependency); 16-30 (moderate dependence);  $\geq$  31 (severe alcohol dependence).

